### **9.2.2 Total Blood Volume**

We will draw a blood volume of 25 cc at the baseline, 7 month, and 14-month visits. The maximum amount of blood drawn over an 8-week period is 25 cc.

## **9.3 Schedule of Procedures/Evaluations: Timing and Definitions**

Follow-up visits at ~7 months and ~14 months following the baseline visit.

### **9.3.1 Screening**

Following oral consent (OCS) for screening (see **Figure** for flow diagram), participants will be asked to complete an iris scan to check for duplicate enrollment (individuals will not be able to enroll more than once). The iris scans are converted by proprietary software into long encrypted codes that are used to identify persons who have participated previously in the study (Iris ID, Inc.: EAC2500 Software and iCAM TD100 dual iris imager. The iris scan system protects participant confidentiality because the iris images are not saved in the system and codes derived from the scans cannot be used to reconstruct iris scan images. Finally, the codes generated by the iris scans at screening

will not be stored – they will only be used to cross-reference with the database to quickly identify individuals who have already participated and prevent such individuals from entering the study a second time.

Participants with no match in the iris scan code database will be asked to answer screening questions.

[figure not shown]
Participants that remain eligible after completing the screening questions, will be asked to provide written informed consent.

Following written informed consent, participant iris scan codes will be registered in the database to prevent duplicate enrollment in the future. Study staff will complete a State of Maryland HIV testing form and provide pre-test counseling.

Participants will be asked to provide blood and urine samples, and have a fingerstick for a rapid HIV test. We will

use the INSTI HIV-1/HIV-2 rapid test (bioLytical Laboratories, Richmond, BC, Canada), a 3rd generation HIV 1/2 test, which is also used by the BCHD. After specimen collection and rapid testing, research staff will provide post-test HIV counseling, discuss eligibility for the cohort study, and offer cohort enrollment to eligible individuals.

Participants with negative HIV test results will be counselled to resume routine testing (every 6 to 12 months) depending on ongoing risk factors. Participants with invalid results will be advised to retest in the next 1 month. Participants with a positive HIV test (and who have not previously tested positive) will be referred to a BCHD facility for confirmatory HIV testing and linkage to care. After HIV post-test counseling, we will make a final eligibility determination on the basis of 1) the screening survey, 2) ability to provide a blood sample, and 3) results of the rapid HIV test. These data will be applied to the study inclusion/exclusion criteria described in **Section 7.1** to determine eligibility to join the cohort.

**Figure. Screening/Enrollment Diagram**

### **9.3.2 *Enrollment***

Participants that are eligible for the cohort will be offered enrollment. Research staff will conduct the baseline visit as soon as possible following screening (usually the same day).

### **9.3.3 *Follow-up***

There will be 2 follow-up cohort visits at ~7 and ~14 months. Study visits will include 1) collection of contact information, 2) an interviewer-administered questionnaire, 3) blood draw, and 4) urine sample. The questionnaire will cover the following domains: socio-demographics (age, race, sex, education, employment, geo-coding, incarceration), substance use (injection and non-injection drugs, alcohol [AUDIT]), drug using network, overdose history, injection practices (frequency, needle/syringe sharing, drugs used), sexual transmission risk behaviors (number of partners, concurrency, condom use, MSM, sex work), depression (PHQ-9), quality of life (SF-12), social support, and resource utilization (SSP, HIV care, HCV care, PrEP, MOUD, other substance abuse treatment modalities, emergency department use, hospitalizations, time and money spent obtaining medical care).

### **9.3.4 *COVID-19 Impact on Study***

The COVID-19 pandemic initially struck Baltimore, MD in March 2020 and had substantial effects on this study. The pandemic led to suspension of both study cohort follow-up visits and the ICV intervention for many months. The study achieved full enrollment (N=720, n=60 at each of the 12 sites) between July 2018 and August 2019. Two cohort follow-up visits were planned at 7 months and 14 months. At the time of pandemic-related shut downs we had completed the 7-month visits at all 12 sites. Additionally, we had completed the 14-month visit at 4 of the 12 sites. We switched to telephone-based follow-up visits, which included the participant survey but not laboratory tests. We also added questions to assess the effects of COVID-19 among the study cohort. We resumed in-person visits in July 2021. For the purposes of this trial, we decided to base primary analyses on the baseline visit and the first follow-up visit (7 months). Although this does not include the longer follow-up that we planned, it includes only data that was collected prior to the pandemic. In secondary analyses we will consider data collected during and after pandemic-related shut downs.

## **10. ASSESSMENT OF SAFETY**

### **10.1 Safety Assessment Overview**

This section provides information on the definition of adverse events (AE), serious adverse events (SAE) and the procedures for reporting. Procedures for prompt reporting of AE and SAE will be standardized across the field sites.

### **10.2 Definition of Adverse Events (AE)**

An AE is any unfavorable and unintended sign (including an abnormal laboratory finding), symptom, or diagnosis that occurs in a study participant during the conduct of the study regardless of the attribution (i.e., relationship of event to medical treatment/study product/device or procedure/intervention). This includes any occurrence that is new in onset or aggravated in severity or frequency from the baseline condition.

### **10.3 Definition of serious adverse events (SAE)**

An SAE is defined as any untoward medical occurrence that:

- Results in death
- Is life-threatening
- Requires inpatient hospitalization or prolongation of existing hospitalization
- Results in persistent or significant disability/incapacity
- Is a congenital anomaly/birth defect
- Is an important medical event that may not be immediately life-threatening or result in death or hospitalization but may jeopardize the patient or may require intervention to prevent one of the other outcomes listed in the definition above).

### **10.4 Adverse Event Procedures and Reporting Requirements**

The research procedures in our study include study visits with cohort participants and key-informant interviews. These research procedures are minimal risk (involve only a blood draw), and do not include a drug or medical device. Furthermore, study sites (or clusters) are the unit of randomization, not individual participants. Participants at intervention sites have access to the intervention (ICV), but are not required to seek or accept the intervention. The intervention itself is being rolled out by the BCHD, and this study is a formalized assessment of the intervention. Finally, the study population of active PWID have substantially higher risks of morbidity and mortality than persons in the general population. Given these considerations, our reporting obligations for the trial focus only on events that are more likely than not to be associated with study procedures (study visits or key-informant interviews). Two types of events will be reportable:

1. Unanticipated problems involving risks to participants or others will be reported to the JHM IRB within 10 working days (unless the event is death, in which case # 2 applies). Such events are defined as:
  - a. The information is unexpected in terms of nature, severity, or frequency, given:
    - i. The research procedures described in the protocol and informed consent document; and
    - ii. The characteristics of the subject population being studied
  - b. The information indicates that the participants or others are at greater risk of harm (including physical, psychological, economic, or social harm) than was previously known or recognized.
2. Deaths of study participants in close association with study procedures will be reported to the IRB within 3 working days.

## **11. CLINICAL MANAGEMENT**

### **11.1 Clinical Management of Adverse Events**

Research staff will interact with participants at study visits and during the intervention (dispensing non-cash incentives). Research staff will refer participants to a clinic or hospital for medical conditions that arise.

### **11.2 Criteria for Permanent Intervention Discontinuation or Premature Study Discontinuation**

Potential reasons for discontinuation of intervention or study are:

- Request by the participant to stop.
- Request of study coordinator if s/he thinks the intervention is no longer in the best interest of the participant.
- At the discretion of the IRB/Ethics Committee, Office for Human Research Protections (OHRP), other government agencies as part of their duties, or investigator

## 12. STATISTICAL CONSIDERATIONS

### 12.1 Overview and General Design Issues

The primary objective of this study is to determine whether provision of an ICV at neighborhood sites, served by the mobile SSP in Baltimore, reduces risk, improves health, and increases uptake of evidence-based services among PWID. We will address this objective with a two-arm, matched-pair, 12-site cluster randomized trial.

Neighborhood sites allocated to the control condition, will continue to receive SSP services. Neighborhood effects will be assessed in cohorts of PWID participants enrolled at each study site, prior to intervention roll-out, and followed for up to 14 months. During the trial, we will collect qualitative data from PWID (who used and did not use ICV services), ICV staff, and other stakeholders. Finally we will collect costing data to facilitate evaluation of cost-effectiveness.

### 12.2 Study Endpoints

Primary and secondary study endpoints will be assessed at follow-up cohort visits on the basis of laboratory testing, structured interviews, and external sources of data, including treatment episodes (emergency department visits, hospitalizations, outpatient clinic visits) captured by Chesapeake Regional Information System for Our Patients (CRISP) and the National Death Index. Exploratory endpoints will be assessed on the basis i) costing data collected during the study, and ii) qualitative key informant interviews.

#### 12.2.1 Primary Endpoint

Composite PWID score (service access, risk behaviors, adverse outcomes). This outcome will be assessed in participants at all visits. To capture the multi-faceted nature of the ICV intervention and the array of health issues relevant to PWID, we developed a composite score that will be captured at baseline and recalculated at each follow-up visit. We developed a scoring rubric (**Appendix**) based on WHO guidelines for evidence-based PWID services, a predictive risk model for HIV seroconversion among PWID developed by the Baltimore-based ALIVE study, the HCV care continuum, and the overdose epidemic.

#### 12.2.2 Secondary Endpoints

- HIV care continuum (among HIV-positive participants).
- Recent HIV testing (among HIV-negative participants).
- PrEP continuum (among HIV-negative participants).
- HCV care continuum (among HCV-positive participants).

- HCV testing (among HCV-negative participants)
- Engagement in MOUD (among all participants).
- Engagement in SSP
- Possession of a naloxone overdose kit (among all participants).
- Injection drug use (among all participants)
- Recent drug use (among all participants) – Urine drug test positive for fentanyl (metabolite), heroin (morphine or 6MAM), cocaine (metabolite), or amphetamines
- Sharing drug paraphernalia (among all participants)
- Non-fatal drug overdoses (among all participants)
- Emergency department use (among all participants).
- HIV seroconversion
- HCV seroconversion
- All-cause mortality (among all participants).

#### **12.2.3 Exploratory Endpoints**

- Qualitative assessments among key stakeholders.
- Costs and cost-effectiveness

#### **12.3 Study Hypothesis**

We hypothesize that the availability of an ICV that provides evidence-based PWID-focused services will reduce risk, improve health, and increase uptake of evidence-based services among PWID.

#### **12.4 Sample Size Considerations**

To estimate the power to correctly reject a null hypothesis, we used simulation methods assuming a normally distributed composite PWID score. We adapted the methods of Arnold et al. for using mixed effects logistic regression random intercepts for cluster (SD = .22) and participant (SD = 1.05) with one baseline and one follow-up assessment, 80% retention, and a similar treatment effect at each follow-up. With an initial sample size of 720 participants, we would have 80% power if the true person-level composite scores were .33 standard deviations higher at follow-up at the target sites than at the control sites, controlling for composite scores at baseline, random variation across study sites, and random variation across individuals. Using Cohen's criteria, this would correspond to a small-medium effect size.

## 12.5 Study Site Selection and Pair Matching

We will use a parallel cluster randomized trial, in which random allocation to the experimental condition occurs at the site- (or cluster-) level rather than at the participant-level. Like other randomized designs, cluster randomized trials are methodologically rigorous and yield strong inferences about intervention effectiveness. Cluster randomized trials are well-suited to implementation research because participant-level randomization is often impractical with multi-faceted or structural interventions and is susceptible to contamination bias in this setting. The SSP vans currently serve 15 neighborhood sites across the city. We will select 12 of the sites to include in the cluster randomized trial. Several factors are relevant to site selection. We must consider proximity of the sites. If two sites are very close together, there may be contamination, where the intervention delivered at one of sites affects the proximal site as well. Where there is a high risk of overlap between two sites, we will exclude one of the sites or consider the two sites to be a single site in the trial.

Because the number of randomly allocated units in this cluster randomized trial is small, we anticipate using a matched-pair design. The idea is to identify pairs of sites that are similar to one another in important characteristics, with one site in each pair randomized to the intervention and the other site to usual care. To assess for good site pairings, we will review all available BCHD data about the different SSP sites – number of clients accessing services each week, client demographic characteristics, and HIV prevalence. Additionally, we will interview current SSP staff to capture qualitative aspects of the different sites. At the conclusion of this process we will identify 12 sites (6 pairs) for the trial. Of note, cohort recruitment at the sites will be staggered, whereby recruitment will begin at the first 2 pair (4 sites), then move to a second set of 2 pair, and finally to a third set of 2-pair.

## 12.6 Randomization and Masking Procedures

Once the randomization scheme is finalized (including consideration of pair-matching) a statistician, who is independent of the study will randomize sites in pairs using a commercial software program. The statistician will withhold results until cohort enrollment is complete or nearly complete for a given pair of sites. When cohort enrollment in a given pair is complete or near complete, the statistician will notify the team of the random assignments for the sites in a given pair. The nature of the intervention precludes masking.

## 12.7 Analysis Plan

### 12.7.1 *Analysis plan for primary and secondary endpoints*

We will estimate the impact of the ICV on the composite primary outcome which incorporates the following: HIV prevention, testing, and treatment; HCV prevention, testing, and treatment; substance use and treatment; overdose; and healthcare utilization (see Appendix). We will also estimate the impact of the ICV on the separate measures that make up the composite outcome, including the HIV care cascade, the PrEP continuum, MAT engagement, and linkage to HCV treatment. The outcomes will be continuous (composite primary outcome), ordinal (HIV care cascade, PrEP continuum, HCV linkage), and dichotomous (MAT), and the analytic samples will vary depending on

the outcome. For all outcomes, the data will have the same structure, with time ( $t$ ) nested within participants ( $i$ ) nested within SSP sites ( $j$ ). The three-level structure of the data will induce correlations in the outcomes within sites and within participants, and this will be addressed by using random intercepts for site and random intercepts for participants. Fixed effects will include covariates for calendar time (a linear, quadratic, spline terms, or indicators as indicated by exploratory data analysis), indicator for 6-month follow-up assessment, a time-varying indicator for ICV exposure status, and follow-up-by-ICV-status interaction terms. This general linear model can be expressed as:

$$\pi_{ijt} = \beta_0 + U_{0i} + U_{0j} + ICV_{ijt}\beta_1 + FU_{ijt}\beta_2 + ICVxFU_{ijt}\beta_3 + \mathbf{x}'_{ijt}\boldsymbol{\gamma} + \mathbf{z}'_j\boldsymbol{\zeta} + \varepsilon_{ijt}$$

where:  $\pi_{ijt}$  denotes the linearized expected outcome for participant  $i$  at SSP site  $j$  on occasion  $t$ ;  $\beta_0$  is the overall intercept;  $U_{0i}$  and  $U_{0j}$  are normally distributed person-level and site-level random intercepts;  $ICV_{ijt}$  is an indicator for participation being at an ICV site,  $FU_{ijt}$  is a binary indicator for the 6-month follow-up assessment;  $ICVxFU_{ijt}$  is an ICV-by-follow-up interaction term;  $\mathbf{x}_{ijt}$  is a vector of participant-level covariates with  $\boldsymbol{\gamma}$  the vector of corresponding fixed-effects regression parameters;  $\mathbf{z}'_j$  is a vector of SSP site covariates (including intervention phase) with  $\boldsymbol{\zeta}$  the vector of corresponding fixed effects; and  $\varepsilon_{ijt}$  are error terms. The null hypothesis of no significant group-by-time interaction at the follow-ups can be tested using a 1-df F-test of  $H_0: \beta_3 = \mathbf{0}$ . The form of  $\pi_{ijt}$  and the expected distribution of the residuals will be specified based on the specific outcome. For the composite outcome, we will use mixed effects linear regression with an identity link function and normally distributed residuals.

The above-described model does not have a coefficient for matched-pair, and therefore “breaks the pairing.” This approach may be more statistically powerful when the matching accounts for little variability among clusters, and we expect that to the case given the limited information that was available for conducting the matching. How much variability is accounted for by the matching will be based on reduction in the variance of the cluster-level random intercept when including fixed effects for matched-pairs, and a likelihood ratio test comparing models with and without fixed effects for matched-pairs.

For ordinal outcomes, such as an individual’s location along the HIV care cascade or PrEP continuum, mixed effects ordinal logistic regression is a natural analytic approach. Such a method assumes an underlying continuum of propensity for viral suppression or PrEP adherence. In a classic example, Aiken and colleagues used ordinal logistic regression in a randomized trial to model movement along a mammography continuum with ordered outcome categories including doing nothing, contacting a healthcare provider, making an appointment, and actually receiving a mammogram—these outcomes parallel the care cascade and PrEP continuum. Gibbons and Hedeker described using ordinal logistic regression in a three-level random effects model, as we propose here.

The ordinal logistic model is also referred to as the proportional odds model as it assumes that ICV exposure has the same effect on transitioning across the various cascade/continuum thresholds. Thus, the interaction between follow-up and ICV status

would be interpreted as the change in the log-odds of being past any given threshold in the care cascade (e.g., recent prescription for ART) with ICV exposure, controlling for other factors in the model, including person-specific and site-specific, random intercepts. In our analyses, we will evaluate the proportional odds assumption through the use of the Score test. If the proportional odds assumption is violated, we will proceed with a nested dichotomies approach using a logit link function. It is also possible that the three-level ordinal logistic model may not converge. In that case, we will also use nested dichotomies. With nested dichotomies, we would first dichotomize outcomes between the first and second steps of the care cascade (or PrEP continuum) and evaluate the effect of the intervention on the odds of being at least linked to care; in a second model limited to those at least linked to care, we would evaluate the effect of the intervention on the odds of being engaged in care; and so forth.

For the dichotomous outcome of MOUD use in the last 30 days, we will follow the same general formula described above using mixed effects logistic regression with a logit link function and a binomial residual distribution. Outcome analyses will be preceded by preliminary analyses examining bias in intervention assignment and potential baseline confounders of the relationship between assignment and the primary outcomes. We shall evaluate and adjust for any potential confounders in adjusted outcome analyses. All analyses will be conducted in Stata and will include the use of the random effects gllamm procedures with Huber/White variance-covariance estimators.

The composite PWID score will be calculated for each participant at each study visit according to the rubric in the **Appendix**, where a higher score indicates higher risk for adverse events or lower use of evidence-based PWID services. At the follow-up visits, we will calculate each participant's change in score from baseline. We will estimate the association between ICV cluster and change in the score with a multi-level linear regression model, similar to that shown above. In a supplementary analysis, we will convert follow-up scores to binary outcomes that indicate whether the score has decreased from baseline (improved) or not. In this case we will use a logistic regression model.

We are aware of the risk of attrition in this study, and our sample size estimates have accounted for up to 20% attrition, despite intensive retention efforts. We will examine whether missingness is associated with observed data using standard methods. If we do identify predictors of missingness (i.e., data are not missing completely at random [MCAR]), we will conduct a second set of outcome analyses using multiple imputation to evaluate the robustness of the primary outcome analyses to missingness and report estimates based on multiple imputation that would be valid based on the assumption that the data are missing at random (MAR) as opposed to not missing at random (NMAR). As missing data are expected to follow multiple distributions, we will impute using chained equations. We will produce imputed datasets ( $m > 10$ ), run outcome analyses on all sets, and derive point and standard error estimates for treatment effects and other parameters from the distribution of estimates from the outcome analyses with imputed datasets. We will implement multiple imputation using the Stata "mi impute chained" and "mi estimate" procedures.

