**Table 1. Comparison of services with the mobile SSP alone (control) and the SSP combined with the ICV (intervention).**

Type of service	SSP (control)	ICV intervention
Risk reduction		
SSP	Confidential (ID-based) SSP using hybrid exchange/distributive model	Same
Overdose prevention /response	SSP program leads city-wide initiative to train and provide naloxone overdose kits to PWID, their friends, and family	Same, although ICV will provide increased opportunities for naloxone kit training and distribution
PrEP	Refer to PrEP program offered at BCHD clinics	Onsite provision of PrEP education, clinical /lab screening for PrEP eligibility, PrEP prescription, and monitoring
HIV care cascade		
HIV testing	Free (non-rapid) HIV and syphilis testing offered on the van once or twice a year	Free rapid HIV testing offered daily
Linkage to HIV care	No routine service	Intervention team tracks care cascade using Data to Care program, peer navigators link clients to care.
ART adherence /viral suppression	No routine service on mobile SSP.	ICV team communicates with HIV treatment providers in city, tracks patients who have lapsed with ART prescription fills, on-site case management to address barriers, laboratory testing on van to assist clinic, ART refills provided
Substance abuse treatment	Referral to buprenorphine- or methadone-based MOUD with dedicated slots for SSP clients	Low-barrier, same-day prescription of buprenorphine, with transition community-based MOUD
Additional PWID services		
HCV care cascade	Referral to BCHD clinics or elsewhere for testing, disease staging, and treatment	HCV antibody and HCV RNA testing on ICV, initiate HCV treatment on ICV with case management support. Referral for advanced liver disease.
Wound care	Referral to primary care provider or emergency department	Wound care-certified NP offers acute and chronic wound care management on the van, with referral for specialized treatment 

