**Table 2. Laboratory testing for cohort participants**

Test	CLIA status	Visits measured	Participants included	
			HIV-negative	HIV-positive
Tenofovir diphosphate concentration in peripheral blood mononuclear cells	Non-certified	V00, V07, V14 (among subset reporting linkage to PrEP)	•	
Hepatitis C virus (HCV) serology	Certified	V00	•	•
HCV RNA	Certified	V00 & V14 (in HCV seropositive only)	•	•
Urine drug screening, high resolution accurate mass spectrometry	Certified	V00, V07, V14	•	•

SCR, screening; V00, baseline visit, V07, 7-month visit; V14, 14-month visit

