## 14. APPENDIX

**Table. Rubric for composite PWID score (service access, risk behaviors, adverse outcomes)**

Score component	Denominator	Category definitions
Service access		
HIV care continuum	HIV positive	0 – Suppressed (HIV RNA <200 c/mL) 1 – Not suppressed, and either i) took ARVs in prior 30 days (self-report) OR ii) had visit with HIV provider in prior 6 months 2 – Not suppressed AND did not take ART in prior 30 days AND did not have visit with HIV provider in prior 6 months (includes those unaware of HIV+ status) at the visit
HIV testing	HIV negative	0 – Had HIV test in past 6 months 1 – Did not have HIV test in past 6 months
PrEP continuum	HIV negative	0 – Used PrEP in prior 6 months (self-report) 1 – Did not use PrEP in prior 6 months
HCV care continuum	HCV positive i. all Ab(+) + RNA(+) or ii. Ab(+) + RNA(-) + treated	0 – HCV treatment history (self-report) and HCV RNA suppressed (<15) 1 – Not suppressed and either treated for HCV OR evaluated by HCV provider in prior 6 months 2 - Not suppressed AND not treated for HCV in prior 6 months AND not evaluated by HCV provider in prior 6 months.
HCV testing	HCV negative i. Ab(-) or ii. Ab(+) + RNA(-) + never treated	0 – Had HCV test in past 6 months 1 – Did not have HCV test in past 6 months
MOUD use	All	0 – Used MOUD in past 6 months 1 – Did not use MOUD in past 6 months
SSP use	Injected in prior 6 months	0 – Used SSP in past 6 months 1 – Did not use SSP in past 6 months
Available naloxone kit	All	0 – Has naloxone kit on person or where drugs used 1 – Does not have accessible naloxone kit
Risk behaviors		
Injection drug use	All	0 – No injection drug use in prior 6 months (self-report) 1 – Injection drug use in prior 6 months
Recent drug use	All	0 – Urine drug test negative for drugs of concern (*see footnote) 1 – Urine drug test positive for one or more drugs of concern (*see footnote)
Sharing injecting equipment	All	0 – No sharing syringe/works OR not using/injecting in prior 6 months 1 – Sharing works (cotton/cooker) only in prior 6 months 2 – Sharing needle/syringe in prior 6 months
Adverse outcomes		

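### If the ordinal model fails, the fallback estimates the ICV effect on HIV suppression only in people linked to care after randomisation, so it can understate or reverse a real benefit

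*Combined protocol and SAP*

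**What the plan says.** The HIV care continuum is a secondary endpoint in HIV-positive participants (Section 12.2.2). Section 12.7.1 analyses it by mixed-effects ordinal logistic regression with random intercepts for site and participant. The ICV-by-follow-up interaction "would be interpreted as the change in the log-odds of being past any given threshold in the care cascade".

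There are two triggers for a fallback. The first is: "If the proportional odds assumption is violated, we will proceed with a nested dichotomies approach using a logit link function". The second is non-convergence of the three-level ordinal model. The first fallback model compares at least linked with not linked. After that, "in a second model limited to those at least linked to care, we would evaluate the effect of the intervention", here on the odds of being engaged in care, and later steps follow the same pattern.

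The Appendix rubric scores the HIV continuum in three levels:

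- Level 0: suppressed.
- Level 1: "Not suppressed, and either i) took ARVs in prior 30 days (self-report) OR ii) had visit with HIV provider in prior 6 months".
- Level 2: neither suppressed nor in care by either criterion.

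Table 1 describes linkage to HIV care at ICV sites as: "Intervention team tracks care cascade using Data to Care program, peer navigators link clients to care". It lists no routine service at control sites.

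**The concern.** Cohorts are recruited before randomisation (Section 7.2), so being linked at follow-up is an outcome of the trial. The ICV acts on it directly. A model restricted to the linked compares two groups that the intervention has itself selected: people linked anyway at control sites, against people linked anyway plus people linked because of the ICV.

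The restriction also changes the question. The main model concerns passing a threshold among all HIV-positive participants. The restricted model drops everyone at level 2 and still presents its result as an intervention effect. The fallback contains no unrestricted suppression model and no caveat on interpretation.

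If the newly linked are suppressed less often than those linked anyway, a real gain in suppression can appear as no effect or as harm. Section 12.7.3 also draws on viral suppression for cost-effectiveness, which calls for an effect in the whole HIV-positive group.

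**Working it through.** The plan gives no linkage or suppression rates and no power figure for this endpoint, so there is no figure of its own to reproduce. Every rate below is assumed.

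**Set-up.** At follow-up, 40% of control participants are linked and 60% of those are suppressed, so 0.40 × 0.60 = 24% overall. The ICV arm has the same people plus a fraction d newly linked, of whom a fraction s are suppressed. Nobody already linked changes.

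- Suppressed, everyone, ICV arm: 0.24 + d·s
- Suppressed among the linked, ICV arm: (0.24 + d·s) / (0.40 + d)

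**Worked case, d = 0.20 and s = 0.40.**

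- Everyone: 0.24 + 0.08 = 0.32. Odds ratio (OR) = (0.32/0.68) / (0.24/0.76) = 1.49.
- Linked only: 0.32/0.60 = 0.533. OR = (0.533/0.467) / (0.60/0.40) = 0.76.

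| d | s | OR, everyone | OR, linked only |
|---|---|---|---|
| 0.20 | 0.40 | 1.49 | 0.76 |
| 0.20 | 0.50 | 1.63 | 0.87 |
| 0.20 | 0.60 | 1.78 | 1.00 |
| 0.20 | 0.70 | 1.94 | 1.15 |
| 0.10 | 0.40 | 1.23 | 0.85 |
| 0.30 | 0.40 | 1.78 | 0.71 |

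**Other assumed rates.** With 60% of controls linked and 70% of those suppressed (42% overall), suppose 15 points more are linked.

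- s = 0.30: everyone 0.465, OR 1.20; linked only 0.465/0.75 = 0.62, OR 0.70.
- s = 0.70: everyone OR 1.53; linked only 1.00.
- s = 0.80: everyone OR 1.62; linked only 1.10.

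**Do the planned random intercepts remove the selection?** The first set-up was simulated with baseline and follow-up visits, and with ICV, follow-up and interaction terms. It used 600 sites of 150 HIV-positive people to show the limiting value. The random-intercept SDs were 0.22 (site) and 1.05 (participant). These come from the composite-score power calculation in Section 12.4 and are only stand-ins for a log-odds model. The interaction ORs were:

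| s | Everyone | Linked visits only (range over 3 seeds) |
|---|---|---|
| 0.40 | 1.66 | 0.75–0.79 |
| 0.50 | 1.85 | 0.87–0.93 |
| 0.60 | 2.06 | 1.01–1.08 |
| 0.70 | 2.29 | 1.18–1.26 |

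A separate simulation of 16,000 people, with no site intercept and no effect on suppression given linkage, gave 1.58–2.28 for everyone and 0.66–0.91 for the linked. The random intercepts do not remove the selection.

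**Trigger and bias can coincide.** In the first set-up with d = 0.20, the linkage OR is (0.60/0.40) / (0.40/0.60) = 2.25, against suppression ORs of 1.49 to 1.94. Proportional odds is therefore false in each of those cases. Whether the Score test would detect it is unknown, because the number of HIV-positive participants is not given.

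**The case against.** - **The quoted second step is engagement in care, not suppression, and the text mentions a recent ART prescription as a threshold.** This is true, and a longer cascade is possible. But Section 12.7.1 treats the HIV cascade as one of the measures making up the composite, which the Appendix scores in three levels. With more levels, more models would be restricted and the selection would remain.
- **Nested dichotomies are a standard decomposition, and linkage × suppression-given-linkage recovers overall suppression.** This is correct: 0.60 × 0.533 = 0.32. The plan does not commit to combining the steps, and it reads the restricted step as an intervention effect.
- **This is a fallback for a secondary endpoint in a subset.** This stands and limits the importance of the point.
- **The example may be extreme.** With 85% of controls linked, 60% of them suppressed, and 5 points newly linked at s = 0.40, the ORs are 1.08 and 0.96. The signs still differ, but the distortion is slight.
- **Precision will be low.** Assume 150 HIV-positive participants, 80% retention, follow-up data only and no clustering. The approximate 95% interval for 0.76 is then 0.27–2.2, and for 1.49 it is 0.67–3.3. A firm false conclusion of harm is unlikely, but imprecision does not remove bias.
- **Cumulative models could also fail to converge, and after a proportional-odds violation there is no single OR to preserve.** Both are fair. The restricted model has the same structure on fewer people, and threshold-specific ORs in everyone still answer the original question.

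**Conclusion.** The concern holds. Every fallback step after the first conditions on a post-randomisation outcome that the ICV targets. Under the assumed rates, a gain in suppression from 24% to 32% (OR 1.49) appears as 0.76.

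The direction is not fixed:

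- If the newly linked do worse than those linked anyway, the benefit is understated or reversed.
- If they do equally well, the sign is not distorted but the overall gain is not shown.
- If they do better, the estimate favours the ICV even though nobody already linked has changed.
- If the ICV does not change linkage, this distortion does not arise.

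The clear case is the HIV continuum at 7 months. As scored in the Appendix, HCV is affected only where 14-month RNA is analysed, because Table 2 schedules HCV RNA at baseline and 14 months only. PrEP has two levels in the rubric and is affected only if more are used. The primary composite, the main ordinal model and the first dichotomy are unaffected. The documents do not show how likely the fallback is to be used.

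**What to change.** In Section 12.7.1, replace the nested dichotomies with cumulative ones. At each threshold, fit the same mixed logistic model for at or beyond that step versus below it, in everyone in the outcome's baseline-defined denominator. For HIV this means two models among all HIV-positive participants: levels 0–1 versus 2, and level 0 versus 1–2. The approach applies under both triggers and keeps the thresholds and population of the main model. Label any step-conditional estimate as descriptive. A partial proportional-odds model is an alternative only when the trigger is a proportional-odds violation, not non-convergence.

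The cost is a change of wording. HIV RNA is already scheduled for HIV-positive participants at baseline, 7 and 14 months (Table 2). The software and the number of HIV models stay the same, and the second model uses all HIV-positive participants instead of the linked subset.
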